iPhone® Helping Evaluate Atrial fibrillation Rhythm through Technology (iHEART) Study (NCT02731326)

IRB approval: August 15, 2020

Study Design

The iPhone® Helping Evaluate Atrial fibrillation Rhythm through Technology (iHEART) study is a single-center, prospective, randomized controlled trial (RCT) (**Figure 1**). The primary aims of the iHEART study are to: (1) Examine the efficacy of mHealth ECG technology (iHEART intervention) on the detection and treatment of recurrent AF as compared to usual cardiac care (control group); (2) Evaluate the quality-adjusted life-years (QALYs) in those in the iHEART intervention as compared to the control group between baseline and 6 months; (3) Determine the impact of behavior altering, motivational text messages on chronic cardiovascular conditions (e.g., hypertension, diabetes) and AF knowledge over 6 months. Participants are randomized to one of two groups: iHEART (intervention group) or usual care (control group). All participants enrolled will be followed for a period of 6 months. This study protocol adheres to the appropriate standards of reporting as stated in the Standard Protocol Items: Recommendations for Interventional Trials statement and facilitates the methodology of the Consolidated Standards of Reporting Trials statement for later dissemination of the results of the outlined RCT.

Study Population

Patients will be screened for eligibility (**Table 1**). Those who meet inclusion criteria will be approached for enrollment after the patient's provider agrees to the study protocol and is willing to receive and review ECG transmissions. The details of the study will be explained in English or Spanish, and patients will be given an opportunity to ask questions before signing informed consent. A copy of the consent form will be given to the patient.

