Inclusion criteria will include documented AF that has been treated in the last 30 days resulting in the restoration of normal sinus rhythm. The operational definition of AF for this study will include the presence of AF captured by the AliveCor® Mobile ECG, a standard 12 lead ECG, Holter, or any other external recording mechanism that documents AF. Over a six-month period, those individuals with \leq 7 days of AF will be considered paroxysmal, and those with greater than 7 days of continuous AF will be defined as persistent AF per the AHA/ACC/HRS guidelines. The main exclusion criteria for participants include documented permanent (chronic) AF, unwillingness to use technology and have one's clinical data collected over the study period, unwillingness to receive and read cardiovascular text messaging three times a week, and patients who have a documented medical history of cognitive impairment.

Data and Safety Monitoring

The study was approved by the Columbia University Medical Center Institutional Review Board. Participants provide written informed consent prior to enrollment and all data collection procedures are in accordance with the Health Information Portability and Accountability Act regulations.

Sample Size

A total of 300 participants with documented AF who are undergoing clinical treatment of their AF with electrical cardioversion, radiofrequency ablation and/or medical management to restore normal sinus rhythm will be enrolled. After a normal rhythm is restored, participants will be randomized to usual cardiac care (n= 150) or usual cardiac care plus the iHEART intervention (n= 150). The population will be recruited from the Columbia University Medical Center (CUMC) cardiac services and will include English and Spanish speaking participants.

Randomization

The randomization process will be performed by a random computer number generator in a one-to-one block allocation ratio. In order to achieve a balance of applicable participant characteristics in both the intervention and control groups, participants will be stratified based on age and gender.

Outcome assessments

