Upon study entry, all relevant clinical data will be collected at baseline and monthly throughout six months via an electronic medical records system review. This will be used to capture and quantify cardiac outcomes in both groups. In addition, all outside medical records will be requested, and participants will be contacted monthly to capture any hospitalizations, cardiac events, or changes in therapy that may occur outside of our center and clinics. AF in the usual care group may be detected during routine follow-ups with providers, as well as during self-evaluations such as a pulse check initiated as a result of participant-reported symptoms or changes in health status. AF may also be captured by a 12-lead ECG, pulse check, or heart sound auscultation during an exam that reveals an irregular heart rhythm. Participants in the usual care group may seek medical evaluation by their providers because of a change in their health status or symptoms (shortness of breath, palpitations, fatigue), which may lead to further cardiac monitoring or testing (e.g., echocardiogram) that may reveal AF. This could include Holter monitoring (24 hour) or extended cardiac monitoring (7-30 days) that may document AF and be the basis for changes in treatments prescribed by their providers (e.g., medication changes or dosage adjustments, cardioversion). In the intervention group, AliveCor® Mobile ECG transmissions will be read daily to detect recurrence of AF or other arrhythmias. All results and any treatment changes due to mobile ECG findings will be recorded over the course of the study period.

All study participants will be asked to complete a series of questionnaires including the Atrial Fibrillation Knowledge Scale (AFKS), the Canadian Cardiovascular Society Severity in Atrial Fibrillation scale (CCS-SAF), the Atrial Fibrillation Effect on Quality of Life (AFEQT), the Control Attitudes Scale-Revised (CAS-R), the Morisky 4-item Self-Report Measure of Medication-Taking Behavior (MMAS-4), the Self-Efficacy for Appropriate Medication Use Scale (SEAMS), the Short Form Health Survey (SF-36 Quality of Life), European Questionnaire 5 Dimensions (EQ-5D), the Patient Health Questionnaire (PHQ-9), and the State Trait Anxiety Inventory (STAI). These measures will be administered to both the intervention and control groups at baseline prior to any procedures, such as a cardioversion or ablation, and again at the 6-month follow-up visit for the purpose of comparison.

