The primary endpoint is detection of recurrence of AF. Secondary endpoints include treatment changes as a result of early detection of AF recurrence, study questionnaire scores at baseline and six months, including QoL, QALYs, and improvement in cardiovascular measures (e.g., blood pressure, glucose levels) and AF knowledge from baseline to 6 months. Outcome assessors will be blinded to group allocation.

Statistical Analysis

We will define and calculate recurrent AF detection rate as the ratio of the number of recurrent AF episodes to the number of person-months of follow-ups. We will compare the difference in recurrent AF detection rate over the six-month study period between the control group and the iHEART intervention group. Analysis of the potential moderating effects of demographic factors (e.g., age, gender, etc.) as well as the difference between the groups will be performed using multivariate Poisson regression.

We will compare the time-to-treatment between the iHEART intervention group and the control group with the application of survival analysis methods. For those who are treated for recurrent AF, the time-to-treatment is the time from beginning of study to the time of treatment. Those who are not treated for recurrent AF will be censored at the end of the sixth month, or the time of death should a subject die before the sixth month. We will apply the Cox proportional hazard model to examine and test the difference in the time-to-treatment between the intervention group and control group, with the adjustment for other potential confounders (e.g., age, gender). QALYs are calculated as follows: for each month of life lived at an EQ-5D index of x , the QALYs will be $x/12=0.0833x$ years. We will calculate QALYs during the 6-month study period for all participants by summarizing QALYs from baseline through sixth month. We will compare QALYs between the iHEART intervention group and the control group using a two-tailed independent sample t-test. To adjust for potential confounders (e.g., age, gender), multivariate linear regression models will be used. Additionally, we will compare change of quality of life (QoL) and symptoms of AF scores (AFEQT, AFKS, EQ5D and CCS-SAF scales, etc.) from baseline to 6 months between the two groups and between those with and without AF using linear mixed models (growth model).

Figure 1. Flowchart for Study Procedures

[figure not shown]

Table 1. Inclusion and Exclusion Criteria

Inclusion Criteria

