- Males and females (English or Spanish speaking) age ≥ 18 years with a prior history of AF in the last 30 days that was treated and normal rhythm restored
- Already utilizes a smartphone prior to enrollment
- Ability to successfully use the AliveCor™ Heart Monitor, capture a baseline ECG, and transmit on the day of enrollment
- Demonstrated ability to receive and read text messages on the day of enrollment
- Willingness to complete the study questionnaires at baseline and 6 months

Exclusion Criteria

- Documented permanent (chronic) AF
- Unwillingness to have their clinical data collected over the study period
- Unwillingness to receive and read cardiovascular text messaging three times a week.

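### Questionnaires are given at two visits only, so the growth model should give way to a two-visit analysis that uses the baseline score efficiently in the randomised comparison

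*Combined protocol and SAP*

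**What the plan says.** Three places agree on the schedule. The Outcome assessments section gives the scales to both groups "at baseline prior to any procedures, such as a cardioversion or ablation" and "again at the 6-month follow-up visit for the purpose of comparison". The Study end-points section lists, among the secondary endpoints, "study questionnaire scores at baseline and six months, including QoL". Table 1 requires "Willingness to complete the study questionnaires at baseline and 6 months". The monthly contacts in the Outcome assessments section collect hospitalisations, cardiac events and therapy changes; no questionnaire is attached to them.

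The Statistical Analysis section then compares change in the AFEQT, AFKS, EQ5D, CCS-SAF and other scores "from baseline to 6 months between the two groups and between those with and without AF", and does so "using linear mixed models (growth model". It does not state random effects, a covariance structure or how the baseline score is handled. QALYs are treated separately, by t-test and linear regression.

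**The concern.** A growth model is normally understood to give each participant an intercept and a slope. With two measurements per participant there is not enough information to estimate how much slopes vary beyond measurement error. If the model is cut back to one that two visits can support, with the arms' baseline means left free, the treatment term becomes the plain difference in change scores. In a randomised comparison that gives away precision which the baseline score, already collected, could supply.

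At stake are the quality-of-life, symptom and AF-knowledge score comparisons, the last being part of Aim 3. Because the model is not specified, the choice of random effects and baseline handling could also be made after the data are seen, across many scales.

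**Working it through.** **Inputs.** From the documents: two questionnaire times; 150 per arm (Sample Size section: "participants will be randomized to usual cardiac care (n= 150) or usual cardiac care plus the iHEART intervention (n= 150"). Not in the documents, so assumed: baseline to 6-month correlation r = 0.3 to 0.9, equal SD at both visits, a true difference of 0.3 SD, two-sided alpha 0.05, no dropout. The plan states no figure for this analysis and no power inputs, so there is nothing of its own to reproduce beyond 150 + 150 = 300.

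**Step 1: identification.** Code time as 0 and 1. Let v0 be the intercept variance, v1 the slope variance, c their covariance and s the residual variance. The observable quantities are:
- Var(baseline) = v0 + s
- Cov = v0 + c
- Var(6 months) = v0 + v1 + 2c + s

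That is three equations for four unknowns (rank 3 of 4). Different values give the same data distribution:

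| s | v0 | v1 | c | Var(baseline) | Cov | Var(6 months) |
|---|---|---|---|---|---|---|
| 0.3 | 0.7 | 0.8 | -0.2 | 1.0 | 0.5 | 1.4 |
| 0.5 | 0.5 | 0.4 | 0.0 | 1.0 | 0.5 | 1.4 |
| 0.6 | 0.4 | 0.2 | 0.1 | 1.0 | 0.5 | 1.4 |

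A slope variance of 0.8 cannot be told from one of 0.2. A random-intercept model has two variance parameters and is identified.

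**Step 2: the group contrast.** In one simulated complete data set (150 per arm, r = 0.5, true difference 0.3 SD), the random-intercept group-by-time term was 0.4991, exactly the difference in mean change. The over-parameterised random-slope fit also converged to 0.4991 (SE 0.110), with log-likelihood -800.849 for both models. The contrast survives; only the split of the variance is arbitrary.

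**Step 3: precision for the randomised arms.** In SD units, with n per arm:
- Change score: Var = (2/n) × 2(1 - r)
- ANCOVA: Var = (2/n) × (1 - r²)
- Ratio = (1 - r²) / [2(1 - r)] = (1 + r)/2

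For r = 0.5 and n = 150: change score (2/150) × 1 = 0.0133, SE 0.115; ANCOVA (2/150) × 0.75 = 0.0100, SE 0.100. Power is approximately Φ(0.3/SE - 1.96).

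| r (assumed) | SE change | SE ANCOVA | Variance ratio | Power change | Power ANCOVA |
|---|---|---|---|---|---|
| 0.3 | 0.137 | 0.110 | 0.65 | 59% | 78% |
| 0.5 | 0.115 | 0.100 | 0.75 | 74% | 85% |
| 0.7 | 0.089 | 0.082 | 0.85 | 92% | 95% |
| 0.9 | 0.052 | 0.050 | 0.95 | about 100% | about 100% |

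Simulation (4,000 runs per value) gave ratios of 0.67, 0.74 and 0.87 at r = 0.3, 0.5 and 0.7, in line with the formula.

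**Step 4: a mixed model can match ANCOVA.** In the data set of Step 2, a two-visit mixed model with a common baseline mean gave 0.4475 (SE 0.0967), against 0.4474 (SE 0.0968) for ANCOVA and an SE of 0.110 for the unconstrained model. The gain comes from using the baseline, not from leaving mixed models.

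**Step 5: AF versus no AF.** These groups are not randomised and may differ at baseline. With an assumed baseline gap of 0.5 SD and no difference in change, the change score returns 0, while ANCOVA returns 0.5 × (1 - r) = 0.35, 0.25 or 0.15 SD at r = 0.3, 0.5 or 0.7. The two methods answer different questions here.

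**The case against.** A reader might infer that the planned analysis cannot be fitted, or that the questionnaire comparisons cannot be answered. The documents do not support that. The plan never mentions random slopes or individual trajectories; its stated target is the group difference in change, which two visits identify, and Step 2 shows the estimate intact even in the over-parameterised fit. The label is wrong for the schedule and the specification is missing, but the estimate is valid and unbiased.

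A reader might also infer that ANCOVA must replace mixed models. It need not: the plan does not fix an unconstrained baseline, and a constrained two-visit mixed model is equally precise. It also keeps participants who miss one visit, whom ANCOVA as usually run would drop.

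The size is assumed. At r = 0.9 the gain is 5% of variance, and even at r = 0.7 power moves only from 92% to 95%. That objection stands as to size. Against it, baseline is taken before cardioversion or ablation and follow-up is six months later, so a correlation near 0.9 should not be presumed.

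Finally, the same sentence covers AF versus no AF, where greater precision is not a sufficient reason to change method. That stands in full and limits the recommendation to the randomised arms.

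**Conclusion.** The point holds in a limited form and is a free improvement, not the correction of an invalid analysis. Individual slope variance is not identifiable from two visits, so the growth label should go. The randomised contrast remains estimable, but in its usual form it forgoes between 35% (r = 0.3) and 5% (r = 0.9) of the change-score variance. These figures rest on equal variances at both visits and on assumed correlations; the power figures rest also on an assumed 0.3 SD effect and no dropout. The reach is the secondary questionnaire scores. The primary endpoint and the QALY analysis are untouched.

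**What to change.** In the Statistical Analysis section:
- Delete the growth-model label.
- For the randomised arms, specify for each scale a two-visit linear mixed model with unstructured covariance, no random slopes and baseline means constrained equal across arms, adjusted for age and gender (the stratification factors). The alternative is ANCOVA of the 6-month score on arm, baseline score, age and gender. Name one of the two in advance.
- State how missing 6-month scores are handled. The mixed model keeps participants missing one visit.
- Keep AF versus no AF as a separate observational analysis of change, without the equal-baseline constraint.

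The cost is a change of wording. No added visits, data or participants are needed.

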Study Intervention

Participants randomized to the iHEART intervention will receive an iPhone® and cellular service plan with unlimited data/text messaging, the AliveCor® Mobile ECG, and Behavioral Altering Motivational (BAM) text messaging three times a week for six months. BAM is an in-house database that automatically sends one-way text messages to the intervention participant related to their AF, as well as two underlying cardiovascular risk factors of their choosing.

AliveCor™ Heart Monitor

The AliveCor® Mobile ECG, an FDA-approved smartphone technology, works through a free application, "Kardia." It captures a highly sensitive (98%), specific (97%), and accurate (97%) single-lead ECG recording through two electrodes on the back of the smartphone[7]. When the application is opened, recording begins automatically when both electrodes make contact with skin (Figure 2). Transmissions are automatically uploaded to the study portal within the

AliveCor® “cloud”. All participants will receive in-person training on the use of the study equipment at enrollment. A return demonstration from the participant to the research coordinator will be required at baseline enrollment. This will include how to capture an ECG daily and in the setting of symptoms, as well as how to record any associated symptoms in the application.

All ECG images and any associated symptoms will be sent via WiFi or cellular network transmission to the AliveCor® cloud. A login will occur daily to the password-protected study database that will be stored on the AliveCor® cloud in order to review and interpret all ECG strips transmitted during the previous 24 hours. Any clinically significant arrhythmias, including AF or other arrhythmias, detected during the daily review of ECGs over the 6-month period will be immediately sent to the provider caring for the participant. The study team will ensure the provider has received the transmission, is aware of any ECG abnormalities, and will then be responsible for communicating such findings.

Smartphone

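### Rhythm at randomisation is not documented, so AF that returned before entry can be counted in the primary recurrence rate, and more often in the intervention arm

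*Combined protocol and SAP*

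**What the plan says.** Study Population requires "documented AF that has been treated in the last 30 days resulting in the restoration of normal sinus rhythm". Table 1 similarly asks for a "prior history of AF in the last 30 days that was treated and normal rhythm restored". Sample Size fixes the order: "After a normal rhythm is restored, participants will be randomized". All three treat restoration as something that has already happened. None asks that it still hold at randomisation.

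One ECG is tied to enrolment. Table 1 asks that the patient be able to operate the heart monitor and "capture a baseline ECG, and transmit on the day of enrollment". The AliveCor section describes the training and adds: "A return demonstration from the participant to the research coordinator will be required at baseline enrollment". No rhythm finding, eligibility consequence or counting rule is attached to this tracing.

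Study end-points makes detection of AF recurrence the primary endpoint. Statistical Analysis turns it into recurrent episodes divided by person-months and compares the arms by Poisson regression. It neither defines an episode nor says how AF present at time zero is handled. Under Outcome assessments, intervention strips are read every day, while AF in usual care comes to light through routine visits, symptoms, pulse checks and provider-ordered tests. The same section places the baseline questionnaires before any cardioversion or ablation.

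**The concern.** A patient whose AF was treated three weeks ago, who returned to sinus rhythm and then relapsed before enrolment, meets every written criterion. Follow-up then starts with AF already present. In the intervention arm an early daily strip will probably show it. In usual care it is found only if a visit, a symptom or an ordered test brings it out. Either way nothing in the plan stops it being counted as a recurrence during follow-up.

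That AF began before the person-time at risk, so it does not belong in a rate whose denominator starts at randomisation. Randomisation balances such patients between arms in expectation, but it does not balance their chance of being counted. The primary contrast would then mix AF arising under follow-up with AF that a common baseline check could have identified equally in both arms.

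**Working it through.** **The plan's own figure.** Sample Size gives 300 participants, 150 per arm. No event rate, effect size or power is stated, so there is no planned rate ratio to reproduce.

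**Inputs from the documents**
- n = 150 per arm (Sample Size).
- 6 months of follow-up (Study Design), so 150 × 6 = 900 person-months per arm if complete.
- Device sensitivity 0.98 (AliveCor section), used as the chance that AF present at entry is found in the intervention arm. This suits continuing AF. Intermittent AF or missed recordings would lower it.

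**Assumptions (not in the documents)**
- λ = 0.05 new counted episodes per person-month in both arms. Setting this equal isolates the contribution of AF present at entry.
- f = proportion in AF at randomisation: 2%, 5% or 10%.
- c = proportion of those found in usual care: 50%, 30% or 10%.
- Each such case is counted once.

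**Formulas**
- New episodes per arm: 0.05 × 900 = 45.
- Intervention count: 45 + 150 × f × 0.98.
- Control count: 45 + 150 × f × c.
- Rate ratio = intervention count / control count, since person-months are equal.

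| f | In AF at entry, per arm | Intervention count | Control count and ratio, c = 50% | c = 30% | c = 10% |
|---|---|---|---|---|---|
| 2% | 3 | 47.94 | 46.50, 1.03 | 45.90, 1.04 | 45.30, 1.06 |
| 5% | 7.5 | 52.35 | 48.75, 1.07 | 47.25, 1.11 | 45.75, 1.14 |
| 10% | 15 | 59.70 | 52.50, 1.14 | 49.50, 1.21 | 46.50, 1.28 |

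With λ = 0.10 the base is 90 per arm and the ratios shrink. At c = 50% they are 97.35/93.75 = 1.04 for f = 5% and 104.70/97.50 = 1.07 for f = 10%.

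**Where the counted cases fall.** The intervention share is 0.98/(0.98 + c): 66% at c = 50%, 77% at c = 30%, 91% at c = 10%.

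**Repeated counting.** If one continuing case were counted three times in the intervention arm and once in control (λ = 0.10, f = 5%, c = 50%), the ratio would be (90 + 3 × 7.35)/93.75 = 112.05/93.75 = 1.20. Counted six times, it would be 134.10/93.75 = 1.43. This comes from the undefined episode, which is a separate gap, but it acts on the same patients.

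**Timing.** Sample Size randomises after rhythm is restored, and Table 1 requires restoration for entry. Outcome assessments puts baseline before cardioversion or ablation. If the enrolment-day ECG belongs to that baseline, it may precede restoration, and AF on it would be expected. Figure 1 is not shown, so the sequence cannot be checked there.

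**The case against.** The strongest reply is that AF which has returned after treatment is recurrent AF, and that finding more of it is what the device is for. This stands in part: these are real events, and a reader who calls them false positives goes too far. The equal-detection model above is also artificial, since a device that finds more existing AF should find more new AF too. It measures one component and does not predict the trial's result. The reply does not cover AF that started before follow-up, because the primary measure is a rate per person-month from study entry and such AF could be established at entry in both arms.

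A reader might infer that these cases would fall almost only in the intervention arm. The documents do not support that. They list many detection routes in usual care over six months, and a 91% share needs control detection of only 10%, a figure given nowhere.

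A reader might also infer that the enrolment ECG tests device skill and nothing else. That is an argument from silence. The tracing is called a baseline ECG and is transmitted, and the daily review described in the AliveCor section does not exempt it. If it is read in both arms, the asymmetry shrinks. The exact statement is that no rhythm use is written down.

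Finally, making that particular tracing an entry gate may not work, because of the timing conflict. This objection stands and shapes the fix.

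**Conclusion.** The point holds in limited form. As written, the plan lets AF present before randomisation enter the primary numerator, and it is more likely to be counted under daily-read ECGs than under usual care. The direction follows from the documents, provided usual care finds fewer of these cases. The size does not, because f, c and λ are all assumed. With λ = 0.05 and 50% control detection, the ratio is about 1.07 at 5% prevalence and 1.14 at 10%. At 2% prevalence it is at most 1.06 over the control detection range tried (10% to 50%). The intervention arm would hold about 66% to 77% of these cases if control detects 50% to 30% of them. If usual care found 98%, the ratio would be 1.00.

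The effect may therefore be small. It is still worth removing, because it touches the primary endpoint and the remedy is cheap. Time-to-treatment also starts at the beginning of the study and so could be affected. That was not calculated, and the conclusion does not rest on it.

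**What to change.** 1. Reconcile Outcome assessments (baseline before cardioversion or ablation) with Sample Size and Table 1 (rhythm restored before randomisation), and state the order of enrolment, ECG and randomisation.
2. Record rhythm at randomisation in both arms, from the mobile ECG already captured, or from a repeat if that tracing precedes restoration.
3. Code AF then present as prevalent in both arms. Do not count it as recurrence in the primary rate until a sinus tracing intervenes.
4. Report the number in AF at entry by arm, with a sensitivity analysis that counts them.

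Under the model above, the contribution of AF present at entry falls to zero and its ratio returns to 1.00. The planned 300 need not change. The cost is one data field, a repeat tracing for some participants, and somewhat fewer counted events: at 5% prevalence and 50% control detection, about 7 of 52 in the intervention arm and 4 of 49 in control. One asymmetry remains, since an intervening sinus tracing is easier to obtain with daily strips. This is a further reason to report these patients separately.
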